7.2.1 Prior to mailing

Provide a description of what procedures will be performed on visit 1 or day 1 or pre-test in order of how these will be done. If your study only involves one session or visit, use this section only and indicate 7.2.2 as not applicable.

We have developed a way to query to EHR to identify patients at PSH St. Joseph's FCM or Women's Health clinics, ages 30-65, who are out-of-date with cervical cancer screening, and who do not have documentation of disqualifying conditions. After generating this list, we will use REDCap to randomize participants to the control arm or intervention arm (2:1). The study team will then prepare mailings of letters (control arm) or letters with postcards (intervention arm) to send to participants.

7.2.2 Mailings

Provide a description of what procedures will be performed on visit 2 or day 2 or post-test in order of how these will be done. If your study involves more than two sessions or visits replicate this section for each additional session or visit (e.g., 7.2.3, 7.2.4, etc.).

Once participants are randomized, they will then be sent a reminder letter in English and Spanish inviting them to schedule a screening. Participants in the intervention arm will receive a modified version of this letter, as well as a pre-addressed, pre-stamped postcard to request an HPV self-sampling kit.

7.3 Duration of Participation

Describe how long subjects will be involved in this research study. Include the number of sessions and the duration of each session - consider the total number of minutes, hours, days, months, years, etc.

The duration of the participation will be up to three months for active monitoring.

7.4 Test Article(s) (Study Drug(s) and/or Study Device(s))

7.4.1 Description

Provide a brief description of all test articles (drugs (including any foods and dietary supplements), devices and/or biologics used in the research including the purpose of their use and their approval status with the Food and Drug Administration (FDA). Include information about the form of the drug product (e.g., tablets, capsules, liquid).

The Evalyn® Brush is a self-sampling kit that screens for HPV, a leading cause of cancer death among women. This tool has recently been FDA approved, but has not been incorporated into national clinical guidelines. This product is a small pink capped brush that can be used to take a sample of cervical cells.

7.4.2 Treatment Regimen

Describe dose, route of administration and treatment duration. Include information about dose adjustments.

Participants will take a sample of their cervix cells that amounts to a few millimeters of bio specimen.

7.4.3 Method for Assigning Subject to Treatment Groups

Describe the randomization process and how the associated treatment assignment will be made.

Not applicable.

7.4.4 Subject Compliance Monitoring

Insert the procedures for monitoring subject compliance.

Subject compliance will be confirmed once their lab results are received from the Penn State Heath Clinical lab.

7.4.5 Blinding of the Test Article

Describe how the test article is blinded.

Not applicable.

7.4.6 Receiving, Storage, Dispensing and Return

7.4.6.1 Receipt of Test Article

Describe how the test article will be obtained and from what source. Describe how the study test article will be packaged along with amounts (e.g., number of tablets/capsules or volume of liquid) and labeling. If drug kits are used, describe all the contents of the kit and associated labeling.

1 HPV self-sampling kit will be sent to the Penn State Heath Clinical lab in a prepaid mailing. Inside the mailing will be the HPV self-sampling kit with the instructions and a Penn State Heath Clinical lab Pathology Services Special Account Requisition form.

7.4.6.2 Storage

Describe the plans to store, handle the test article so they will be used only on subjects and only by authorized investigators. Describe storage temperature requirements and how temperature will be monitored and recorded.

Before HPV self-sampling kits are sent to study participants, they will be stored in a locked cabinet in the Department of Family and Community Medicine offices at [name]. Kits mailed to the lab will be disposed of after analysis.

7.4.6.3 Preparation and Dispensing

Describe how the test article will be assigned to each subject and dispensed. Describe the steps necessary to prepare the test article. Include where the test article preparation will be done and by whom. Fully describe how the study treatment is to be administered and by whom.

Before it is sent to the participant, the Penn State Heath Clinical lab Pathology Services Special Account Requisition document will be labeled with the participant's ID #, date of birth, and sex. The Mailing will include the HPV self-sampling kit with the instructions, a summary explanation of research, Penn State Heath Clinical lab Pathology Services Special Account

Requisition form. Also, the package will include a prepaid and labeled mailing to send the kit and Pathology Services Special Account Requisition document to the Penn State Health Clinical lab. Participants will need to include the date and time of sample collection on the Requisition form.

7.4.6.4 Return or Destruction of the Test Article

Describe the procedures for final reconciliation of the test article supply at the end of the study and whether the test article is to be shipped back to a source or destroyed on site.

HPV self-sampling kits will not be returned to participants. The samples will be analyzed and the kits will be destroyed by the Penn State Health Clinical lab once analysis is complete.

7.4.6.5 Prior and Concomitant Therapy

Describe what prior and/or concomitant medical therapy will be collected. Describe which concomitant medicines/therapies are permitted during the study. Describe which concomitant medicines are not permitted during the study.

Not applicable.

8.0 Subject Numbers and Statistical Plan

8.1 Number of Subjects

Indicate the maximum number of subjects to be accrued/enrolled. Distinguish between the number of subjects who are expected to be enrolled and screened, and the number of subjects needed to complete the research procedures if applicable (i.e., numbers of subjects excluding screen failures.)

The study seeks to have 1,211 participants. There will be 807 participants randomized into the control arm and 404 into the intervention arm.

8.2 Sample size determination

If applicable, provide a justification of the sample size outlined in section 8.1 to include reflections on, or calculations of, the power of the study.

We assume a 15% response rate from the control group, i.e., in response to a standard reminder letter, for a final $n=122$.¹⁷ We further assume a 30% response rate for the intervention group, i.e., requesting an HPV self-sampling¹⁸ kit, for a final $n=122$ for this group. In total, we expect at least 244 participants to respond to their reminders to receive cervical cancer screening.

8.3 Statistical methods

Describe the statistical methods (or non-statistical methods of analysis) that will be employed.

We will calculate the proportion of participants who obtain cervical cancer screening (in the Penn State Health St. Joseph's FCM or Women's Health clinics or with self-collected samples for HPV testing) by arm within three months of the initial mailing. We will use chi-squared tests to compare these proportions, using an alpha of .05 and a beta of 0.80.

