1.2 Primary Study Endpoints

State the primary endpoints to be measured in the study.

Clinical trials typically have a primary objective or endpoint. Additional objectives and endpoints are secondary. The endpoints (or outcomes), determined for each study subject, are the quantitative measurements required by the objectives. Measuring the selected endpoints is the goal of a trial (examples: response rate and survival).

The primary objective is to test the screening differences in control arm (i.e., receiving the standard reminder letter) versus the intervention arm (i.e., receiving a modified reminder letter plus postcard to request HPV self-sampling kit). The purpose is to assess the impact of mailing HPV home sampling kits to patients in need of cervical cancer screening on HPV screening rates.

The primary end point of 1) Completion of cervical cancer screening 2) Use of home cervical cancer screening kit will be evaluated over a three month time period after reminder letters are mailed.

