1.3 Secondary Study Endpoints

State the secondary endpoints to be measured in the study.

The secondary endpoint is overall cervical cancer screening of people mailed a letter.

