Based on this information, self-sampling for HPV testing may be a viable option for cervical cancer screening, particularly among women who do not obtain regular screening in a clinical setting. However, all previous studies have been conducted in a highly-controlled, well-resourced research context. We propose a study using real-world procedures that could pragmatically be adopted in primary care clinics, i.e., evaluating a reminder letter with a post card option to request an HPV self-sampling kit.

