5.4.6 Debriefing

Explain whether and how subjects will be debriefed after participation in the study. If subjects will not be debriefed, provide a justification for not doing so. Add any debriefing materials to the study in CATS IRB.

Not applicable.

5.5 Informed consent will not be obtained – request to completely waive the informed consent requirement

Review “HRP-410-Checklist -Waiver or Alteration of Consent Process” to ensure that you have provided sufficient information.

5.5.1 Indicate why the research could not practicably be carried out without the waiver of consent

Currently, patients do not need to provide informed consent to receive reminders to obtain guideline-recommended clinical procedures. Requiring participants to provide consent would critically reduce the sample size. More importantly, requiring potential participants to consent to receive information about cervical cancer screening could give them the impression that screening is somehow “new” or “experimental,” which could lead to patients who are out-of-date with cervical cancer screening to avoid scheduling a screening.

5.5.2 Describe why the research involves no more than minimal risk to subjects.

Participants will receive a letter directing them to receive a guideline-recommended procedure that is considered standard of care. These procedures do not post more than minimal risks to subjects.

5.5.3 Describe why the alteration/omission will not adversely affect the rights and welfare of subjects.

The rights and welfare of subjects will be maintained because they will still have the option of determining whether or not they want to schedule a cervical cancer screening.

5.5.4 If the research involves using identifiable private information or identifiable biospecimens, describe why the research could not be practicably be carried out without using such information or biospecimens in an identifiable format.

Our outcomes analysis will assess (1) participation in cervical cancer screening during the follow-up period (yes or no), and (2) whether any follow-up procedures were indicated for that patient. The follow up period will consist of three months after the mailing. We will assess differences in these outcomes for participants who receive the standard of care letter versus a modified letter with an option for HPV self-sampling. If we did not use identifiable health information, we would not be able to link the letter type to clinical outcomes.

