7.1 Study Design

Describe and explain the study design.

Invitation letters will be sent out by a study team member to Penn State Health St. Joseph patients who meet the inclusion/exclusion criteria. Participants will receive either (1) a standardized letter informing them that they are out-of-date and should schedule an appointment for their cervical cancer screening (control arm) or (2) a modified version of this letter, plus a pre-addressed postcard to request an HPV self-sampling kit (intervention arm). Kits will be mailed out to those that indicate they want to receive one along with the HRP-586 consent form. Participants will mail self-collected cervical samples to the PSH Hershey lab for processing. A sample is stable for up to 6 months at room temperature: <https://www.sciencedirect.com/science/article/pii/S2405852118300089>. If we receive test kits returned after that timeframe, we will discard the sample and exclude those results. If negative result, patient will be contacted by a study physician with results. If positive result for low-risk HPV, patient will be contacted by a study physician to schedule a Pap test. If positive result for high-risk HPV, patient will be contacted by a study physician to schedule a colposcopy. Scheduling a Pap or Colposcopy test is standard of care for a low-risk or high-risk HPV result, respectively. The study team will monitor receipt of cervical cancer screening across the two arms.

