15.0 Resources Available

15.1 Facilities and locations

Identify and describe the facilities, sites and locations where recruitment and study procedures will be performed.

If research will be conducted outside the United States, describe site-specific regulations or customs affecting the research, and describe the process for obtaining local ethical review. Also, describe the principal investigator's experience conducting research at these locations and familiarity with local culture.

Participants will be recruited through collaboration with St. Joseph's Family and Community Medicine and Women's Health clinics. Participant will be identified through a previously-developed EHR data pull and recruited from their active patient files.

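### Section 8.3 counts provider screening only at two clinics but counts every kit test, so if the outside share is above zero and similar in both arms, a larger share of control-arm screening is missed

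*Combined protocol and SAP*

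**What the plan says.** The analysis rule is in 8.3. The proportion screened is formed from tests in St. Joseph's FCM or Women's "Health clinics or with self-collected samples for HPV testing) by arm within three months of the initial mailing", and the arms are compared with chi-squared tests.

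The endpoint is worded more widely elsewhere:

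- 1.2 gives the primary endpoint as "Completion of cervical cancer screening 2) Use of home cervical cancer screening kit will be evaluated over a three month time period", with no place named.
- 1.3: "The secondary endpoint is overall cervical cancer screening of people mailed a letter".
- 5.5.4 restates the outcome as "participation in cervical cancer screening during the follow-up period (yes or no".

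On capture, 7.1 says "The study team will monitor receipt of cervical cancer screening across the two arms" but does not say by what means. For kits it says "Participants will mail self-collected cervical samples to the PSH Hershey lab for processing". Kits are offered to the intervention arm only (7.2.2). Control women are told to contact their primary care provider (1.1, 4.2.1); the two clinics are not named as the place to go. Women are eligible as patients of either clinic (3.1), and 15.1 adds: "Participant will be identified through a previously-developed EHR data pull and recruited from their active patient files".

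**The concern.** All control-arm screening is provider-collected, so all of it is subject to the place limit. In the intervention arm, some screening is by kit and is seen wherever the woman would otherwise have gone. Completeness of capture can therefore depend on arm. A woman in Women's Health whose primary care provider practises elsewhere could follow the control letter exactly and still be counted as unscreened.

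What is at stake is whether an observed difference is added screening or screening moved to a place the study can see. The hypothesis in 1.1 is about the screening rate, so this distinction matters. The plan collects nothing that would let a reader check it.

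**Working it through.** **Inputs from the documents.** Control rate 15% and intervention rate 30% (8.2, where the 30% is described as kit requests; it is taken here as the planned screening rate). 807 control and 404 intervention women (8.1). Chi-squared test at alpha 0.05 (8.3), taken as two-sided.

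**Inputs assumed, because the documents do not give them.** f, the share of provider screening done outside the two clinics: 5%, 10%, 20%. k, the percentage points of intervention-arm screening done by kit: 2.5 to 10 under no effect, 10 to 20 at the planned effect.

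**The plan's own figure.** For 15% v 30%, two-sided 0.05, 80% power, 1:1 and no continuity correction, the standard formula gives 121 per arm, against the stated 122. Then 121/0.15 = 806.7 and 121/0.30 = 403.3, which round up to the planned 807 and 404. With all 807 and 404 women analysed, power at 15% v 30% exceeds 99.9%.

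**Formulae.** Let p1 and p2 be the true rates, D = p2 − p1, and o1 and o2 the points of screening done outside the two clinics in control and intervention.

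- Observed rates: p1 − o1 and p2 − o2. Bias in the difference: o1 − o2.
- With equal f: o1 = f·p1 and o2 = f(p2 − k). The missed share is f in control and f(p2 − k)/p2 in intervention, which is smaller whenever f and k are above zero.
- Bias in the difference is then f(k − D). The observed ratio is p2/p1 + kf/[p1(1 − f)].

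**No true effect, 15% v 15%, equal f.** Chance of p<0.05 (pooled z, normal approximation, 807/404):

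| f | k=2.5 | k=5 | k=7.5 | k=10 |
|---|---|---|---|---|
| 5% | 5.07% | 5.21% | 5.44% | 5.74% |
| 10% | 5.22% | 5.78% | 6.66% | 7.87% |
| 20% | 5.86% | 8.18% | 11.98% | 17.23% |

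One cell worked through, f=20% and k=5:

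- Observed control 15 × 0.8 = 12%; observed intervention 5 + 10 × 0.8 = 13%.
- Pooled rate (807 × 0.12 + 404 × 0.13)/1211 = 12.33%. Null SE 0.02004, so the critical difference is 1.96 × 0.02004 = 0.0393. SE under the observed rates 0.02027.
- Rejection: Φ[(0.01 − 0.0393)/0.02027] + Φ[(−0.01 − 0.0393)/0.02027] = 0.074 + 0.008 = 0.082.

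Exact binomial enumeration agrees within 0.0015.

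**Where there is no bias, or it reverses.**

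- If kits draw only women who would have used the two clinics, with f=20% in control, then o1 = o2 = 3 points, the observed rates are 12% v 12%, and rejection stays at 5.0%.
- If the modified letter raises outside visits, for example o1 = 3 and o2 = 4, the observed rates are 12% v 11% and the bias is −1.0 point.
- Break-even under no effect: the bias vanishes when the outside share among provider-screened intervention women is f·p/(p − k), where p is the common true rate. At f=20% that is 3/12.5 = 24%, 3/10 = 30% or 3/5 = 60% for k = 2.5, 5 or 10.

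**Planned effect, 15% v 30%, true ratio 2.0.**

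| f | k | Observed rates | Ratio | Bias in difference |
|---|---|---|---|---|
| 10% | 10 | 13.5% v 28.0% | 2.07 | −0.5 points |
| 10% | 15 | 13.5% v 28.5% | 2.11 | 0 |
| 10% | 20 | 13.5% v 29.0% | 2.15 | +0.5 points |
| 20% | 10 | 12.0% v 26.0% | 2.17 | −1.0 points |
| 20% | 15 | 12.0% v 27.0% | 2.25 | 0 |
| 20% | 20 | 12.0% v 28.0% | 2.33 | +1.0 points |

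Power stays above 99.9% in every row. In women, at f=20% and k=15, control misses 807 × 0.15 × 0.20 = 24 of 121 screens (20%) and intervention misses 404 × 0.15 × 0.20 = 12 of 121 (10%).

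**The case against.** The best defence is that 8.3 simply makes a general endpoint operational: a specific counting rule does not contradict broader wording. Nothing in the documents shows that outside screening occurs. Participants are patients of these clinics, and for FCM patients the primary care provider may well be in the counted clinic, so f may be small. The trial's premise in 2.1 is that kits help "particularly among women who do not obtain regular screening in a clinical setting"; if kits are purely additional, k = D and the difference is unbiased. The plan names no ratio, the one measure that is always inflated under equal f. The 17.2% needs f=20%, no effect, and kits replacing two thirds of all screening.

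Most of this stands, and it limits the size of the problem. It does not remove it. The rule in 8.3 measures something narrower than the stated endpoint, the narrowing applies unequally to the two routes of screening, and one route exists in only one arm. A small f is plausible but untested, and the plan as written yields no data on it.

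**Conclusion.** The point holds in its conditional form. If the outside share is above zero and similar in both arms, and kits are used, a larger share of control-arm screening is missed. That is algebra and does not depend on the values chosen.

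The effect on the result is less certain. The absolute difference favours the kit arm only if the kit offer lowers outside screening. It is unbiased if kits are purely additional or draw only from the two clinics, and the bias reverses if the modified letter raises outside visits. The point matters most if the true effect is small or absent, and for any ratio reported; at the planned effect the test result would not change. The problem is probably modest, and worth correcting because the correction is cheap. Confidence is medium, since f and k are assumptions throughout.

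**What to change.** In 8.3, count any cervical cytology or HPV test documented in the health system's electronic record, at any site and including outside results on file. Apply the same pull to both arms. Date tests by specimen collection within the existing three-month limit; 7.4.6.3 already asks for the collection date on the kit requisition. Keep the two-clinic-or-kit count as a sensitivity analysis, and report by arm the number of tests found outside the two clinics, which helps show whether capture differed.

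If a wider pull is not feasible, state in 1.2 that the endpoint is screening at the two clinics or by kit, and limit the conclusion to that.

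The cost is a broader query than the two-clinic one in 4.0 and 7.2.1, a few lines in 8.3, and perhaps a minor IRB modification, because 6.2.2 justifies record access mainly by eligibility (5.5.4 does cover linkage to outcomes). The study is unfunded (16.1), so the effort is a real consideration. Tests never sent to the health system would still be missed and should be stated as a limitation. If half of the outside tests were recovered (an assumption), f is halved and the no-effect rejection rates fall to 5.1-5.7% for f=10% and 5.2-7.9% for f=20%.

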1.0 Objectives

1.1 Study Objectives

Describe the purpose, specific aims or objectives. State the hypotheses to be tested.

The objective of this study is to evaluate the effectiveness of offering self-sampling for high-risk human papillomavirus (HPV) testing in increasing participation in cervical cancer screening.

Specifically, we will determine if women who are out-of-date for cervical cancer screening will be more likely to seek screening if offered the option to complete a self-sampled HPV test compared to standard of care. Eligible patients at Penn State Health St. Joseph (seen through Family and Community Medicine and through Women's Health) who are out-of-date with cervical cancer screening will be randomized to either a control arm or an intervention arm (2:1). Women in the control arm will receive a letter notifying them that they need to be screened and they should contact their primary care provider, according to standard clinical procedures (standard of care). Women in the experimental arm will receive (1) a slightly modified version of this letter informing them of a self-sampling option and (2) a pre-addressed post card to return to the study team if interested in self-sampling. Women who return the post card will then receive, via mail, a self-sampling kit to obtain a cervical sample for an HPV test.

For both arms, women whose cervical cancer screening test (collected by a provider or by the participant herself) indicate the presence of high-risk HPV will be directed to follow-up procedures following standard clinical practice.

Hypothesis: Women notified of a need for cervical cancer screening by letter who are offered self-sampling for cervical cancer screening will have a higher rate of screening that women notified by letter alone.

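### Clinic and age are known before randomisation but are not used in allocation or analysis: an optional, no-cost gain in precision that is small

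*Combined protocol and SAP*

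**What the plan says.** Section 1.1 draws women from two sources within one health system: those "seen through Family and Community Medicine" and those seen through Women's Health. Sections 4.0, 4.2.4 and 7.2.1 describe the EHR query. It selects on clinic, age 30–65, being out of date for screening, and the absence of disqualifying conditions.

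In 7.2.1, once the list exists, "we will use REDCap to randomize participants to the control arm or intervention arm (2:1". No stratification factor or block is named there. Section 7.4.3, where the template asks for the assignment method, is marked as not applicable.

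The analysis in 8.3 is the proportion screened "by arm within three months of the initial mailing". The comparison is "We will use chi-squared tests to compare these proportions", "using an alpha of .05 and a beta of 0.80". No covariate, stratum, effect measure or interval is specified.

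**The concern.** Two clinics with different kinds of patient feed the trial, and screening in those clinics counts towards the endpoint alongside mailed self-samples. Clinic and age could plausibly predict whether a woman is screened within three months. Where a baseline variable predicts the outcome, adjusting for it narrows the interval around the treatment difference and needs no more participants. Both variables are held for every woman before allocation, so no new data are needed.

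Two things are at stake. One is a little precision. The other is pre-specification: if 8.3 stays silent, any adjustment made later is post hoc. As written, the section also commits to proportions and a test but not to an estimated difference with its uncertainty, which is what an effectiveness question needs.

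**Working it through.** **Inputs from the documents**
- 8.1: "There will be 807 participants randomized into the control arm and 404 into the intervention arm", so 1,211 in total.
- 8.2: "We assume a 15% response rate from the control group" and "We further assume a 30% response rate for the intervention group". The second rate is defined as requesting a kit.
- 8.3: alpha 0.05, taken as two-sided. The 0.80 given as beta is read as power.

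**Assumed, because the documents give no figure**
- Odds ratio for clinic 1.3 (weak) to 2.7 (strong).
- Odds ratio for age 1.1 to 1.3 per SD.
- Clinics of equal size, independent of age.
- An alternative intervention rate of 20%, used only to show a case where power is not saturated.

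**1. The plan's own sample size.** The usual pooled formula for 15% versus 30%, 1:1, without continuity correction, gives 121 per arm (8.2 states 122). Dividing by the response rates, 121/0.15 = 806.7 → 807 and 121/0.30 = 403.3 → 404. The stated numbers reproduce.

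**2. Unadjusted power at 807/404.** With difference d, pooled standard error s0 and unpooled standard error s1, power = Φ[(d − 1.96 s0)/s1].
- 15% versus 30%: s0 = 0.02438, s1 = 0.02603, and (0.15 − 1.96 × 0.02438)/0.02603 = 3.93. Power = 99.996%.
- 15% versus 20%: s0 = 0.02271, s1 = 0.02354, and (0.05 − 1.96 × 0.02271)/0.02354 = 0.233. Power = 59.2%.

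**3. Share of variance explained by clinic and age.** I took a logistic model with two equal clinics and normally distributed age, with the intercept set so that each arm has its stated mean. R² is the variance of the predicted probability divided by p(1 − p).

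| Association | R², arm at 15% | R², arm at 20% |
|---|---|---|
| Weak (1.3; 1.1) | 0.33% | 0.42% |
| Strong (2.7; 1.3) | 3.72% | 4.65% |

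**4. Effect on the variance of the risk difference, 15% versus 20%.**
Unadjusted: 0.15 × 0.85/807 + 0.20 × 0.80/404 = 0.0001580 + 0.0003960 = 0.0005540.
- Weak: (0.0001580 × 0.0033 + 0.0003960 × 0.0042)/0.0005540 ≈ 0.4%.
- Strong: (0.0001580 × 0.0372 + 0.0003960 × 0.0465)/0.0005540 ≈ 4.4%.

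**5. In women, interval width and power.**
- Weak: 1,211/0.996 − 1,211 ≈ 5 women. Strong: 1,211/0.956 − 1,211 ≈ 56 women.
- 95% CI half-width: 1.96 × 2.354 = 4.61 points unadjusted. Multiplying by √0.996 gives 4.60 and by √0.956 gives 4.51.
- Power: 59.2% unadjusted, 59.4% weak, 61.1% strong.

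**6. At the planning rates.** Even if adjustment removed 10% of the variance, power would move only from 99.996% to 99.999%, a change of less than 0.01 percentage point.

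**7. Chance imbalance in clinic mix.** SD of the between-arm difference = √[0.25 × (1/807 + 1/404)] = 3.0 points. With an assumed 10-point gap in uptake between clinics, a one-SD imbalance moves the estimate by 0.03 × 10 = 0.3 points, against a standard error of about 2.4 points.

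**The case against.** The strongest reply is that nothing here is broken. An unadjusted chi-squared test is valid under randomisation, and its standard error already allows for chance imbalance, so imbalance and a wider interval are one effect and not two harms. At the plan's own rates the gain is nil. The prognostic strength is assumed, and the endpoint counts mailed self-samples as well as clinic visits, so clinic may predict less well in the intervention arm. The 20% rate appears nowhere in the documents. It does not follow from 30% being a kit-request rate, because clinic screening in that arm also counts. For an unfunded pragmatic feasibility study, a simple test is a defensible choice.

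All of this stands, and it limits the point to a suggestion. It does not remove the case for naming covariates in advance when they cost nothing, or for reporting a difference with an interval, which depends on no assumed association.

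Three stronger readings are tempting and not supported:
- **A reader might infer that the last-screen date is also in the query**, since being out of date implies some screening record. Adding time overdue, at an assumed odds ratio of 1.2 to 1.8 per SD, would raise the variance cut to about 1–9% (16 to 124 women). No section names that date as a query field or data item, and the list may hold only a yes/no flag.
- **A reader might infer that allocation is unstratified.** The documents only fail to specify stratification.
- **A reader might infer that the primary result would be biased or the test invalid.** Neither follows from omitting covariates in a randomised comparison.

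**Conclusion.** The point holds as an optional free improvement of low severity. With the two variables the documents show to be available, adjustment would cut the variance of the risk difference by about 0.4% to 4.4%, worth about 5 to 56 women out of 1,211. It would lift power by at most about 2 points in the assumed 15% versus 20% case. At 15% versus 30% it changes nothing of practical importance. These sizes rest on the assumed odds ratios and equal-sized clinics; a weaker association or a more lopsided clinic split would shrink them. Whether 30% is a realistic completion rate is a separate sample-size question and is not settled here.

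**What to change.** - **7.2.1 and 7.4.3:** state that REDCap allocation is 2:1 within strata defined by clinic, with a rule for assigning any woman attached to both clinics. Replace the not-applicable entry in 7.4.3 with this description.
- **8.3:** make the primary result the risk difference with 95% CI, standardised over the trial population from a logistic model with arm, clinic and age (continuous). Standardising keeps the risk difference as the estimand; an adjusted odds ratio on its own would change it. Keep the chi-squared test as the unadjusted supporting analysis.
- **Time since last screen:** add it only if the EHR list holds the date, with an indicator for women who have no recorded prior screen. Settle this before allocation.

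The cost is a REDCap setting, a few sentences of text and a few lines of analysis code. Clinic and age need no new data and no additional participants. If allocation has already begun, the 8.3 change can still be made, provided it is fixed before outcomes are compared by arm.
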